3.4.2 Secondary Endpoints

- EnSite Precision™ Cardiac Mapping System Assessment
 - o Ease of Use
 - o Overall procedure time
- AutoMark feature Assessment
 - o Clinical Utility of the automated RF marker placement
 - o Ease of Use of the automated RF marker placement

3.5 Inclusion and Exclusion Criteria

A subject, who meets all of the inclusion criteria, and none of the exclusion criteria, is eligible to participate in this registry.

All subjects enrolled in the registry (including those withdrawn from the registry or lost to follow-up) will be accounted for and documented, assigning an identification code linked to their names, alternative identification or contact information.

This log will be kept up to date throughout the registry by the principal investigator or his/her authorized designee. To ensure subject privacy and confidentiality of data this log must be maintained throughout the registry at the site.

To participate in this registry, the subject must meet all of the following inclusion criteria:

3.5.1 Inclusion Criteria

Subjects are eligible for registry participation if they meet all of the following inclusion criteria:

- Patients indicated for a cardiac EP mapping and ablation procedure using a 3D mapping system
- Over 18 years of age
- Ability to provide informed consent for registry participation and be willing and able to comply with the protocol described evaluations

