Devices used:	
All devices must have CE mark and will be used according to their Instructions for Use (IFU).
 
This comprises: The EnSite Precision™ Cardiac Mapping System and software v2.0, which consists of:
 
 - EnSite Precision™ software 2.0 - EnSite Precision™ Module, Sensor Enabled - EnSite Precision™ Surface Electrode Kit - AutoMap™ Module - AutoMark feature - Advisor™ FL Circular Mapping Catheter, Sensor Enabled™ and/or FlexAbility™ SE Ablation Catheter 
Additional tools that may be used in this registry (per physician's discretion), include, but are not limited to:
 
 - Tacticath™ Ablation Catheter - FlexAbility™ Ablation Catheter - MediGuide™ Platform - Other commercially available catheters to facilitate EP procedures 
The EnSite™ Amplifier and Display Work Station, required to support the system, will not be evaluated under the scope of this registry.

Registry Population	
A patient becomes a subject once he/she has been fully informed about the registry, has agreed to participate and signed & dated the Informed Consent Form (ICF).
 
Any patient undergoing a cardiac EP mapping and ablation procedure, using the EnSite™ Precision Cardiac Mapping system, is considered eligible.

Inclusion/Exclusion Criteria	
Inclusion Criteria
 
 - Patients indicated for a cardiac EP study and ablation procedure using a 3D mapping system - Over 18 years of age - Ability to provide informed consent for registry participation and be willing and able to comply with the protocol described evaluations 
Exclusion Criteria
 
 - Contraindication to anticoagulation - Presence of thrombus

Clinical Investigational Plan

	
 - Implanted with mechanical prosthetic heart valve - Recent (<3 months) myocardial Infarction or unstable angina or coronary artery by-pass - Pregnant or nursing - Individuals whose willingness to volunteer in a registry, in the judgement of investigator or public authorities, could be unduly influenced by lack of or loss of the autonomy due to immaturity, or mental disability, or adverse personal circumstances, or hierarchical influence

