3.6.2 Point of Enrollment

Subjects are considered enrolled in the registry from the moment the subject has provided written Patient Informed Consent. (Refer to section 3.7 for the Informed Consent Process).

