12.0 STATISTICAL CONSIDERATIONS

12.1 Statistical Design, Hypotheses, Method and Analytical Procedures

This is a multi-center, observational, prospective registry. The objective of the registry is to assess and characterize the use and performance of the EnSite Precision™ Cardiac Mapping System and EnSite Precision™ Software v2.0 (The System) in a variety of electrophysiological (EP) procedures and clinical settings.

The endpoints for characterizing and evaluating the objective are as following:

Primary Endpoints:

- EnSite Precision™ Software v2.0 Assessment
 - Accuracy of geometry: Proportion of subjects with accurate geometry
 - Overall system stability: Proportion of subjects with overall system stability
 - Unrecoverable shifts: Proportion of subjects whose map could not be recovered

- Automap™ Module Assessment
 - Mapping time associated with (re-)mapping one or multiple arrhythmias in a single subject with a variety of catheters; mapping time will be summarized (using mean, median, standard deviation, minimum and maximum across arrhythmia types, and for each type of arrhythmia as appropriate) for the following modules:
 - Manual
 - AutoMap™
 - TurboMap™
 - Point density associated with (re-)mapping one or multiple arrhythmias in a single subject with a variety of catheters; mapping points collected and used will be summarized (using mean, median, standard deviation, minimum and maximum across arrhythmia types, and for each type of arrhythmia as appropriate)

Secondary Endpoints:

- EnSite Precision™ Cardiac Mapping System Assessment
 - Ease of Use: Proportion of subjects in whom the mapping system was reported to be excellent, very good, good, poor and N/A
 - Overall Procedure time: will be summarized using mean, median, standard deviation, minimum and maximum

- AutoMark feature Assessment
 - Clinical Utility of the automated RF marker placement: proportion of subjects where the AutoMark feature assisted in identifying gaps in lesion lines
 - Ease of Use of the automated RF marker placement: proportion of subjects where the AutoMark feature was easy to use

Analysis method:

The analysis population will include subjects who have signed the Informed Consent Form and undergone the CIP defined EP study and ablation procedure. Endpoints will be summarized based on available data or measurements in the analysis population, as appropriate.

Clinical Investigational Plan

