12.3 Pass/Fail Criteria to be applied to the Results of the Registry

The purpose of this registry is to characterize data collected in the population indicated for a cardiac EP study and/or ablation procedure using a 3D mapping system.

Pass/Fail criteria do not apply to this study.

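### Eligibility statements disagree on the mapping system, and the analysis population in 12.1 and 12.8, read literally, drops procedures in which EnSite Precision failed before ablation

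*Combined protocol and SAP*

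**What the plan says.** **Eligibility.** The body of the plan (3.5.1) includes "Patients indicated for a cardiac EP mapping and ablation procedure using a 3D mapping system". The synopsis inclusion list is equally generic: "Patients indicated for a cardiac EP study and ablation procedure using a 3D mapping system". The Registry Population row of the same synopsis is narrower: "Any patient undergoing a cardiac EP mapping and ablation procedure, using the EnSite™ Precision Cardiac Mapping system, is considered eligible". Section 3.5 makes the listed criteria decisive: "A subject, who meets all of the inclusion criteria, and none of the exclusion criteria, is eligible to participate in this registry". Section 12.3 describes the registry's population in passing as the "population indicated for a cardiac EP study and/or ablation procedure using a 3D mapping system".

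**Enrollment.** Under 3.6.2, "Subjects are considered enrolled in the registry from the moment the subject has provided written Patient Informed Consent". Table 2 in 5.2 allows 10 days from enrollment to baseline and 14 more to the procedure.

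**Analysis.** Section 12.1 states: "The analysis population will include subjects who have signed the Informed Consent Form and undergone the CIP defined EP study and ablation procedure". Section 12.8 repeats this in nearly the same terms, after saying that everyone who consents counts as enrolled. Section 12.9 uses the data available within that population and imputes nothing.

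**Intended device.** Several places tie the registry to EnSite Precision with software v2.0: the Devices Used row of the synopsis, Table 1 in 4.1, the site description in 8.1, and the opening and endpoint list of 12.1. Section 5.5 ties the procedure to the EnSite Precision instructions for use.

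**The concern.** There are two linked problems.

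First, the criteria that decide eligibility do not name the device under evaluation, while the population row does. A patient who consents and is later mapped on another 3D system fails no listed criterion. The route in 5.3 for consented subjects who turn out to be ineligible therefore does not apply, and the subject has already been counted. The screening tool does not clearly close the gap, since 5.10 describes it as working on arrhythmia history.

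Second, the analysis population is defined by completion of EP study and ablation, not by exposure to the system. Three primary endpoints are proportions of subjects: accurate geometry, overall stability, and maps that could not be recovered. Their natural denominator is every subject in whom the system was used. If a system failure ends the procedure before ablation, the failure removes the subject from both numerator and denominator. The plan itself foresees such events: the list of anticipated events in 7.2.1 includes map shifts, system shutdown, and an error that forces the procedure to be cancelled.

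**Working it through.** **1. The plan's own figure.** Section 12.2 wants at least 50 subjects per arrhythmia type and expects ventricular tachycardia (VT) in 10%. 50 / 0.10 = 500, as stated. The figure contains no allowance for subjects who cannot be evaluated.

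**2. Four kinds of procedure traced through the text.** All four subjects have consented and meet the listed criteria, so all are enrolled.

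| Procedure | Population row (1.0) | Analysis population, 12.1 and 12.8 |
|---|---|---|
| A. EnSite Precision v2.0 used, ablation done | met | in |
| B. EnSite Precision v2.0 started, procedure ends before ablation | met as planned, procedure incomplete | out, read literally |
| C. EnSite Precision v2.0 started, abandoned, ablation done on another system | met in part | unclear |
| D. EnSite Precision never started, another system used | not met | probably out, but not stated |

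D turns on what the CIP-defined procedure means. The procedure is described in 5.5, which refers to the EnSite Precision instructions for use, so the natural reading excludes D. B turns on the requirement that ablation was undergone, and there the literal reading works against the registry's purpose. C is not settled by either sentence.

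**3. Direction and size of the loss from B.** Let n be the procedures in which mapping was started, x those with an unrecoverable shift, and k the number of those x that ended before ablation.

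- All started procedures: x / n.
- As the plan reads: (x − k) / (n − k).
- Difference: k(n − x) / [n(n − k)]. This is positive whenever k > 0 and x < n, and never exceeds k / n.

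The documents give neither x nor k. Assume n = 500 and, as the extreme case, that every shift ended its procedure (x = k):

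| Assumed k | All started | As the plan reads |
|---|---|---|
| 5 (1%) | 5/500 = 1.0% | 0/495 = 0% |
| 10 (2%) | 10/500 = 2.0% | 0/490 = 0% |
| 25 (5%) | 25/500 = 5.0% | 0/475 = 0% |

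The proportion with a stable system moves the other way by the same arithmetic. A procedure that ends early for a reason unrelated to the system need not bias the result in this way; losing it mainly costs information.

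**4. Places taken by D.** Let q be the share of enrolled subjects never mapped with EnSite Precision v2.0. The documents do not give q, so it is assumed. Expected VT = 0.10 × 500(1 − q). The probability is the binomial chance of at least 50 VT subjects among 500(1 − q). Enrollment for 500 evaluable subjects is 500/(1 − q), rounded up.

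| q (assumed) | Places used | Expected VT | P(at least 50 VT) | Enrollment for 500 evaluable |
|---|---|---|---|---|
| 0 | 0 | 50.0 | 0.52 | 500 |
| 2% | 10 | 49.0 | 0.46 | 511 |
| 5% | 25 | 47.5 | 0.37 | 527 |
| 10% | 50 | 45.0 | 0.24 | 556 |
| 20% | 100 | 40.0 | 0.06 | 625 |

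The 0.52 in the first row comes from the missing allowance in 12.2, not from the eligibility wording. Only the fall from that row belongs to this point.

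**The case against.** The strongest reply is that the plan leaves no real doubt about the device. Devices Used, Table 1, 5.5, 8.1 and 12.1 all point to EnSite Precision, and all but 5.5 name software v2.0 as well. Section 8.6 selects investigators with experience of it. Mapping on another system would depart from the plan and be a deviation under 6.2. This stands: it reduces the eligibility conflict to a matter of wording, and makes it likely that other-system cases are already outside the analysis population.

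A reader might infer that a subject switched to another system cannot be withdrawn. The documents do not support that: the reasons in 5.11 are not exhaustive, the investigator may withdraw a subject with a reasonable rationale, and a form exists for any withdrawal before the procedure. A reader might also infer that 12.1 is silent on the system. It is not: it opens by naming the system and the software version. Only its population sentence leaves them out.

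It can also be said that the registry tests no hypothesis (12.10) and has no pass/fail criterion (12.3), that 500 is a ceiling, and that failed procedures would remain visible, since 3.5 accounts for all enrolled subjects and 7.2 collects serious adverse events and device effects from the procedure onward. That is fair, but it does not repair the primary endpoints. In a descriptive registry the reported proportions are the result, and 12.1 computes them within the analysis population only.

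Finally, rewording the inclusion bullet would not stop a switch on the day of the procedure, which can fall up to 10 + 14 = 24 days after consent. This is correct, and it is why the population definition matters more than the bullet. None of these replies answers the exclusion of started procedures that end before ablation.

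**Conclusion.** The concern holds in two parts of unequal weight. The inclusion lists and the synopsis population row conflict, but the intended device is clear from the rest of the plan. The more serious part is that 12.1 and 12.8, followed literally, remove started procedures that end before ablation. When the system caused the early end, this makes stability and unrecoverable shifts look better than they were, by up to k/n: 1 percentage point for every 5 such procedures among 500 started.

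The actual size is unknown. The documents give no frequency for failed or abandoned mapping, or for use of another system; the percentages above are illustrations and not estimates. The conclusion assumes that undergoing the procedure means that ablation took place. If the sponsor means attempted procedures as well, the bias disappears, but the text should say so.

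Two stronger readings are not supported. A reader might infer that data from another system will be pooled into the EnSite results, for example as manual mapping time. Section 12.1 reports manual mapping within the AutoMap assessment, nothing says that other systems' data enter there, and the case report forms and procedure guidelines are kept under separate cover. A reader might also infer that the synopsis row and the inclusion lists conflict over software version. None of them names a version; v2.0 comes from the device and site sections and from 12.1.

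**What to change.** 1. In 1.0 and 3.5.1, bring the first inclusion bullet into line with the population row by naming the EnSite Precision Cardiac Mapping System with Software v2.0. The passing description in 12.3 can be aligned at the same time, though nothing depends on it.
2. In 12.1 and 12.8, define the analysis population as consented subjects in whom mapping with that system and version was started. State that this includes procedures in which it failed, was abandoned, or the procedure was cancelled.
3. Exclude subjects in whom it was never started, and report their number.

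The planned 500 need not change. The cost is a few sentences and perhaps one case report form item recording system, version and whether mapping was started, if this is not already captured. A few consented subjects leave the analysis population. Some started but incomplete procedures will lack mapping-time data, which 12.9 already handles by using what is available. The stability figures may look slightly less favourable.

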3.5.2 Exclusion Criteria

Subjects are not eligible for registry participation if they meet any of the following exclusion criteria:

- Contraindication to anticoagulation
- Presence of thrombus
- Implanted with mechanical prosthetic heart valve
- Recent (<3 months) myocardial infarction or unstable angina or coronary artery by-pass
- Pregnant or nursing

Clinical Investigational Plan

- Individuals whose willingness to volunteer in a registry, in the judgement of investigator or public authorities, could be unduly influenced by lack of or loss of the autonomy due to immaturity, or mental disability, or adverse personal circumstances, or hierarchical influence

3.6 Subject Population

3.6.1 Subject Screening

All subjects presenting at the site will be screened by a member of the registry team previously trained on the CIP and delegated to do so.

Subjects who do not meet the inclusion/exclusion criteria will not be eligible to participate in this registry.

Subject's enrollment will be validated via the screening tool provided by the sponsor.

Subjects meeting the inclusion/exclusion criteria, and after obtaining confirmation via the screening tool, will be fully informed about the registry and asked to participate in the registry. In the case the subject agrees, a duly signed and dated Informed Consent Form (ICF) will be obtained.

3.6.2 Point of Enrollment

Subjects are considered enrolled in the registry from the moment the subject has provided written Patient Informed Consent. (Refer to section 3.7 for the Informed Consent Process).

3.7 Informed Consent Process

3.7.1 General process

All subjects will be consented, as required by applicable regulations and the center's ethics committee / institutional review board (EC/IRB) (where applicable). Informed consent must be obtained from each subject prior to any registry related activities, other than those related to screening. The consent form must be signed and dated by the subject and by the person obtaining the consent.

The principal investigator or his/her authorized designee will conduct the informed consent process. This process will include a verbal discussion with the subject on all aspects of the registry that are relevant to the subject's decision to participate in the registry.

The subject will be provided with the informed consent form that is written in a language that is understandable to the subject and has been approved by the center's EC/IRB. Failure to obtain informed consent from a subject prior to registry enrollment should be reported to St. Jude Medical within 5 working days and to the reviewing center's EC/IRB consistent with the center's EC/IRB reporting requirements.

3.7.2 Special circumstances for informed consent

3.7.2.1 Subject unable to read or write

Informed consent will be obtained through a supervised oral process if a subject or legally authorized representative is unable to read or write. An independent witness will be present throughout the process. The written informed consent form and any other information will be read aloud and explained to the prospective subject or his/her legally authorized representative and, whenever possible, either will sign and personally date the informed consent form. The witness also signs and personally dates the informed consent form attesting that the information was accurately explained and that informed consent was freely given.

Clinical Investigational Plan

4.0 DEVICES USED

4.1 Device Description

SJM, sponsor of this registry, will ensure that the registry will only start after full CE certification of the EnSite Precision™ System has been obtained, and copies of the CE-certificates and final Instructions for Use have been sent to the relevant ECs/IRBs if required by local regulations.

Table 1: Description of Proposed Devices

Device Component	Model/Type/Version/Reference	Regulatory status
EnSite Precision™ Software	V2.0 H702496	CE Marked
EnSite Precision™ Module, Sensor Enabled	H702473	CE Marked
EnSite Precision™ Surface Electrode Kit	EN0020-P	CE Marked
AutoMap™ Module	V1.0 H702499	CE Marked
AutoMark feature	V1.0	CE Marked
Advisor™ FL Circular Mapping Catheter, Sensor Enabled™	D-AVSE-D10-F20	CE Marked
	D-AVSE-DF10-F20	
	D-AVSE-D10-F15,	
	D-AVSE-DF10-F15	
FlexAbility™ SE Ablation Catheter	A-FASE-D	CE Marked
	A-FASE-F	
	A-FASE-J	
	A-FASE-DD	
	A-FASE-FF	
	A-FASE-JJ	
	A-FASE-DF	
A-FASE-FJ		

Descriptions and Instructions for Use are available separately.

Additional tools that may be used in this registry (per physician’s discretion), include, but are not limited to:

Clinical Investigational Plan

- Tacticath™ Ablation Catheter
- FlexAbility™ Ablation Catheter
- MediGuide™ Platform
- Other commercially available catheters to facilitate EP procedures

4.2 Device Accountability

[figure not shown]
Only commercially available shelf-stock will be used

No specific device accountability procedures will be followed.

5.0 PROCEDURES

5.1 Registry Flow Chart

Figure 2: Flow Chart

Clinical Investigational Plan

5.2 Procedures

The registry will be conducted in accordance with the CIP. All parties participating in the conduct of the registry will be qualified by education, training, or experience to perform their tasks and this training will be documented appropriately.

The registry will not commence until St. Jude Medical receives written approval from the EC/IRB (if required by local regulations) and relevant regulatory authorities and all required documents have been collected from the site(s).

Table 2: List of all specific activities/procedures

Visit / Activity	Enrollment	Baseline (Max 10d after Enrollment)	Procedure (Max 14d after Baseline)	Pre-Discharge (Max 7d after Procedure)
Eligibility check	X			
Informed Consent Process	X			
Demographics		X		
Arrhythmia History		X		
Cardiac History		X		
Procedure indication		X		
Previous Arrhythmia Treatments		X		
12-Lead ECG		X		X
Medication		X		X
Physical examination		X		X
Mapping of Cardiac Structures			X	
Catheter Ablation			X	
Fluoroscopy images			X	
Export Study data (USB)			X	
User Experience			X*	
Adverse Event			(X)	(X)
Deviation		(X)	(X)	(X)
Withdrawal		(X)	(X)	(X)
Death			(X)	(X)

(X) if applicable

* Once to be completed by every physician performing a procedure

Clinical Investigational Plan

5.3 Enrollment Visit

The following enrollment activities will be performed after the subject has been screened including using the screening tool - and found eligible per advice of the tool - and must occur before any registry procedure/visit.

- The principal investigator or delegated study personnel are responsible for screening all potential subjects to determine subject eligibility for the registry
- Record enrollment information (name of the registry, date of consent and Inclusion/exclusion confirmation) in the hospital records and complete and submit the Enrollment form in a timely manner (recommended within 5 days)
- Notification of enrollment to the sponsor will take place when the sponsor receives the enrollment form

If a subject does not meet all inclusion criteria or meets any of the exclusion criteria, the subject cannot participate in the registry, even if they have provided consent, and will not be enrolled.

In case the subject was already consented to participate in the registry, but does not meet inclusion/exclusion criteria, the following actions will be taken.

If registry procedure has not occurred:

- Document enrollment information (name of the registry, date of consent and inclusion/exclusion) in the hospital records; complete the Enrollment and Withdrawal Forms. The form must be authorized / approved by the principal or delegated investigator.
 - o Inform the subject about the withdrawal.
 - o The EC/IRB and CA should be notified appropriately about any deviations with regards to obtaining the informed consent.

If registry procedure has occurred:

- Document enrollment information (name of the registry, date of consent and inclusion/exclusion) in the hospital records; complete the Enrollment and Withdrawal Forms. The form must be authorized / approved by the principal or delegated investigator.
 - o Complete study deviation for inclusion/exclusion not met
 - o The EC/IRB and CA should be notified appropriately about any deviations with regards to obtaining the informed consent.

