6.2 Adherence to the Clinical Investigational Plan

A deviation is defined as an event where the clinical investigator, site personnel, sponsor or sponsor representative did not conduct the registry according to the Clinical Investigational Plan, EC/IRB requirements or the Investigator Agreement. The investigator is not allowed to deviate from the CIP, except as specified under emergency circumstances.

In some cases, failure to comply with the CIP may be considered failure to protect the rights, safety and well-being of subjects, since the non-compliance exposes subjects to unreasonable risks. For example, failure to adhere to the inclusion/exclusion criteria: these criteria are specifically defined by the Sponsor to exclude subjects for whom the device is not beneficial and the use involves unreasonable risks. This may be considered failure to protect the rights, safety and well-being of the enrolled subject. Similarly, failure to perform safety assessments intended to detect adverse events may be considered failure to protect the rights, safety and well-being of the enrolled subject. Investigators should seek minimization of such risks by adhering to the CIP.

Simultaneously, in the event that adhering to the CIP might expose the subject to unreasonable risks, the investigator is also required to protect the rights, safety and well-being of the subject by intentionally deviating from the requirements of the CIP, so that subjects are not exposed to unreasonable risks.

It is the responsibility of the investigator to provide adequate medical care to a subject enrolled in a registry.

Regulations require that the PI maintain accurate, complete, and current records, including documents showing the date of and reason for every deviation from the Clinical Investigational Plan. Relevant information for each deviation will be documented on a Deviation Case Report Form. The site will submit the CRF to St. Jude Medical.

Clinical Investigational Plan

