7.1.5 Serious Adverse Device Effect (SADE)

Adverse device effect that has resulted in any of the consequences characteristic of a serious adverse event.

7.2 Procedure for Assessing, Recording and Reporting Adverse Events, Complaints, Adverse Device Effects, Serious Adverse Events and Serious Adverse Device Effects

Clinical Investigational Plan

Safety surveillance within this registry and the safety reporting, both performed by the investigator, starts at the Procedure Visit and will continue until the last visit has been performed, the subject is deceased, the subject/investigator concludes his participation into the registry or the subject/investigator withdraws the subject from the registry, except as otherwise specified in the CIP.

For the purpose of this registry, all Serious Adverse Events (regardless of relatedness) and all Adverse Device Effects (regardless of severity) will be documented and reported via an eCRF to the sponsor immediately but no later than 72 hours after becoming aware of the event.

All complaints for SJM products must be reported to SJM Post Market Surveillance. The investigator should notify their SJM representative or SJM Postmarket Surveillance Department as soon as possible after becoming aware of a complaint by email to [contact] or calling [name].

Device related and/or procedure related events/complaints will be further assessed by SJM within SJM Postmarket Surveillance system.

Records relating to the subject's subsequent medical course must be maintained and submitted (as applicable) to the Sponsor until the event has subsided or, in case of permanent impairment, until the event stabilizes and the overall clinical outcome has been ascertained. Adverse events will be monitored until they are adequately resolved. The status of the subject's condition should be documented at each visit.

Subjects will be carefully monitored during the registry for possible required AEs. Any reportable AE will be followed to a satisfactory resolution, until it becomes stable, or until it can be explained by another known cause(s) (i.e., concurrent condition or medication) and clinical judgment indicates that further evaluation is not warranted. All findings relevant to the final outcome of an AE must be reported in the patient's medical record.

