12.8 Procedures that take into account all the Data

All subjects who have signed the consent of this registry will be considered enrolled in the study and are eligible for the data summary and analysis. The analysis population will include subjects who have signed the consent form and undergone the CIP defined EP and ablation procedure.

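### Treated subjects later found ineligible are withdrawn, so new non-fatal adverse events before pre-discharge need not be recorded, although these subjects stay in the analysis population

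*Combined protocol and SAP*

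**What the plan says.** Four parts of the plan bear on a consented subject who is found, after the procedure, not to meet the eligibility criteria.

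- **Section 5.3 (Enrollment Visit).** The general rule is that "the subject cannot participate in the registry, even if they have provided consent, and will not be enrolled". Two branches follow. Both tell the site to "complete the Enrollment and Withdrawal Forms", with authorization by the principal or delegated investigator. Where the procedure has occurred, the branch adds "Complete study deviation for inclusion/exclusion not met". It does not mention the pre-discharge visit, continued safety reporting or analysis status.
- **Section 7.2 (adverse event procedures).** Safety surveillance "starts at the Procedure Visit and will continue until the last visit has been performed", or until one of several other events. One of these is that "the subject/investigator withdraws the subject from the registry, except as otherwise specified in the CIP".
- **Sections 12.1 and 12.8.** Section 12.8 reads: "The analysis population will include subjects who have signed the consent form and undergone the CIP defined EP and ablation procedure". Section 12.1 gives the same rule. Neither makes eligibility or non-withdrawal a condition. Section 12.8 also counts every consented subject as enrolled, as does section 3.6.2.
- **Section 6.2.** The criteria are described as set by the sponsor to "exclude subjects for whom the device is not beneficial and the use involves unreasonable risks".

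The synopsis (Data Collection) adds that system performance will be assessed from procedure data and adverse events.

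**The concern.** Withdrawing an ineligible subject before the procedure costs nothing, because there has been no exposure. The post-procedure branch uses the same instruction for someone who has been exposed. That person leaves prospective safety reporting at withdrawal but still counts in the denominator of any adverse event summary.

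Two things are at stake. First, the subjects affected are those the eligibility criteria were written to keep out, for example because of thrombus, a contraindication to anticoagulation or a recent infarction. Registry reporting may stop early in a group where events would be of particular interest. Second, a subject who is counted but not fully observed can only lower an observed event proportion relative to full capture.

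The plan also gives two answers on whether such a subject is enrolled at all. That affects the accounting of subjects in the final report.

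**Working it through.** The plan states no figure on this point, so the check is a side-by-side reading.

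**Step 1. Does section 5.3 withdraw the subject?** Yes. The Withdrawal Form is required in the post-procedure branch and is authorized by an investigator, so this is withdrawal by the investigator in the sense of section 7.2.

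**Step 2. Does withdrawal end surveillance?** Yes, unless the plan specifies otherwise. Section 7.2 allows for exceptions, but none for treated ineligible subjects appears in 5.3, 5.6, 5.11, 6.2 or 7.3.

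**Step 3. What is still captured?**

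| Item | Captured? | Source |
|---|---|---|
| Reportable events from the Procedure Visit up to withdrawal | Yes | 7.2 |
| Course of reportable events already identified | Yes, to resolution | 7.2 |
| Deaths from the Procedure Visit onward | Yes; the sentence has no cut-off at withdrawal | 7.3.1 |
| Product complaints | Yes, through post-market surveillance | 7.2 |
| New non-fatal SAEs and ADEs after withdrawal | Not required | 5.3 with 7.2 |

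**Step 4. How long is the gap?** Section 5.6 sets pre-discharge within 7 days of the procedure. The gap is the time from withdrawal to pre-discharge, so it lies between 0 and 7 days. It is 0 if ineligibility is found at or after pre-discharge.

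**Step 5. Is the subject still analyzed?** Yes. Sections 12.1 and 12.8 require only consent and the procedure. Section 12.9 uses available data without imputation, so an unrecorded event becomes a non-event in any summary of events over subjects.

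**Step 6. Which summaries are touched?** The endpoints in 3.4 and 12.1 are geometry accuracy, system stability, unrecoverable shifts, mapping time, point density, procedure time, ease of use and AutoMark utility. They arise from the procedure or from user ratings, before this branch of 5.3 can apply. Adverse events are not a listed endpoint. They enter through the synopsis statement and the general provision for counts and percentages in 12.1.

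**Step 7. Is enrollment status consistent?** No. Section 5.3 says such a subject is not enrolled despite consent. Sections 3.6.2 and 12.8 say that consent enrolls.

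**Step 8. Can the effect be sized?** Not from the documents, which give neither a number of ineligible treated subjects nor an event rate. A ceiling can be shown only on assumed inputs: 1% to 5% of 500 subjects affected (5 to 25), SAE risk 10% in them and 4% in the rest, and every one of their events lost.

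- 25 affected: full capture (475 × 0.04 + 25 × 0.10)/500 = 21.5/500 = 4.3%; total loss 19/500 = 3.8%.
- 5 affected: full capture (495 × 0.04 + 5 × 0.10)/500 = 20.3/500 = 4.06%; total loss 19.8/500 = 3.96%.

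The differences are 0.5 and 0.1 percentage points. By Step 3 the true loss under these assumptions would be smaller, because events during the procedure and up to withdrawal are reportable.

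**The case against.** The strongest case against is that little is lost. Surveillance begins at the procedure itself, known events are followed up, deaths and complaints have their own reporting lines, and the window is short. Section 5.3 does not say when a withdrawal takes effect, and Table 2 lists Withdrawal, Adverse Event and Deviation together at Pre-Discharge, so a site could complete all three at that visit. No adverse event proportion is defined in section 12.1, no hypothesis is tested and no pass/fail rule applies. Withdrawal ends registry data collection, not clinical care.

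Most of this stands and limits the size of the point. It does not close the gap: a site that withdraws the subject promptly is following 5.3 and has no duty under 7.2 to report a new non-fatal event afterwards.

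Three stronger readings are tempting and are not supported:

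- A reader might infer that all post-procedure safety data on these subjects are lost. Step 3 shows otherwise.
- A reader might infer that the plan declares every such subject to be at unreasonable risk. Section 6.2 describes the purpose of the criteria and hedges what follows from a breach. Sections 8.2 and 8.4 say that care follows local practice and that the registry adds no risk.
- A reader might infer that the analysis population itself is undefined. Sections 12.1 and 12.8 agree on it. The conflict is over enrollment status.

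One further objection affects the remedy. Inability to consent and unduly influenced willingness are themselves eligibility failures (3.5.1, 3.5.2). A rule that kept every ineligible subject until consent is withdrawn would continue collecting data on doubtful consent.

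**Conclusion.** The point holds in limited form. Read together, sections 5.3 and 7.2 allow new non-fatal SAEs and ADEs to go unrecorded between withdrawal and pre-discharge in treated subjects whom 12.1 and 12.8 still analyze. Any adverse event proportion reported could therefore be slightly understated, and it falls in a group the plan meant to exclude on grounds that include risk. The procedural primary endpoints are essentially unaffected.

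The size cannot be established from the documents. The 0.1 to 0.5 point range above is a worst case on assumed inputs and should not be quoted as an estimate. The conclusion assumes that at least some ineligibility is discovered after the procedure but before pre-discharge, and that sites act on 5.3 at that time. The inconsistency between 5.3 and both 3.6.2 and 12.8 on enrollment status needs no such assumption. The change is worth making because it is cheap.

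**What to change.** 1. **Section 5.3, branch where the procedure has occurred.** Record the eligibility deviation, but continue SAE and ADE data collection through the existing pre-discharge visit. Make two exceptions: the subject withdraws consent, or the ineligibility concerns the validity of consent.
2. **Section 5.3, general sentence on participation and enrollment.** Reconcile it with 3.6.2 and 12.8, so that the plan gives one answer on whether a consented but ineligible subject is enrolled.
3. **Section 12.8.** State that treated, validly consented subjects later found ineligible are included in the analysis population, and that their number is reported. A sensitivity table without them is optional in a descriptive registry.

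This concerns data collection only and changes no aspect of care. The cost is a few sentences of text and, per affected subject, one pre-discharge form for a visit already in Table 2.
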